7.8. Week 10 (Visit 8)—Cohort B only

- Perform Corneal Slit Lamp Safety Exam (Section 6.7.9)
- Collect samples for urine pregnancy test, if applicable (Section 6.6)
- Investigational Product Intravitreal Injection (Section 6.8)
- Prescribe artificial tears and/or lubricating ointment (Section 6.9)
- Collect concomitant medications (Section 6.4)
- Collect adverse events (Section 6.5)

7.9. Week 12 (Visit 9)

- Perform BCVA (Section 6.7.1)
- Perform LLVA (Section 6.7.2)
- Perform Full Ophthalmic Examination (Section 6.7.7)
- Collect Wide Field Color and Autofluorescence Fundus Photographs (Section 6.7.8)
- Collect Macular Optical Coherence Tomography (Section 6.7.6)
- Collect Dark-Adapted Chromatic Perimetry (Section 6.7.5)
- Collect Macular Integrity Assessment (MAIA) (Section 6.7.3)
- Collect concomitant medications (Section 6.4)
- Collect adverse events (Section 6.5)
- Collect Full-field electroretinography (ERG) (Section 6.7.4)

7.10. Week 16 (Visit 10)

- Perform BCVA (Section 6.7.1)
- Perform LLVA (Section 6.7.2)
- Perform Full Ophthalmic Examination (Section 6.7.7)
- Collect Wide Field Color and Autofluorescence Fundus Photographs (Section 6.7.8)
- Collect Macular Optical Coherence Tomography (Section 6.7.6)
- Collect Dark-Adapted Chromatic Perimetry (Section 6.7.5)
- Collect Macular Integrity Assessment (MAIA) (Section 6.7.3)
- Collect concomitant medications (Section 6.4)
- Collect adverse events (Section 6.5)

8. ADVERSE EVENT REPORTING

AEs will be collected from the time the subject signs the informed consent form through 30 days after the last IP administration.

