- 1) Best Corrected Visual Acuity (BCVA): Change in BCVA will be assessed using a normally illuminated ETDRS (Early Treatment Diabetic Retinopathy) chart.
- 2) Low-luminance visual acuity (LLVA): Change in Low-luminance visual acuity (LLVA) and the low luminance deficit (LLD) will be assessed. The LLD is defined as the difference between the BCVA and LLVA. LLVA will be assessed using a 2.0 log unit neutral density filter while reading a normally illuminated ETDRS (Early Treatment Diabetic Retinopathy) chart.
- 3) Macular Integrity Assessment (MAIA) Microperimetry: Central retinal sensitivity will be assessed using MAIA microperimetry using a standard 10-2 test grid with a Goldman size III stimulus of various intensities presented on a mesopic background (4 apostilbs).
- 4) Full field Electroretinography (ffERG): Change in dark-adapted flash ($0.01 \text{ cd} \cdot \text{s} \cdot \text{m}^{-2}$) b-wave amplitudes will be analyzed. Testing will be performed using a standard International Society for Clinical Electrophysiology of Vision (ISCEV) protocol.
- 5) Dark-Adapted Chromatic Perimetry: Change in dark adapted retinal sensitivity (dB) to the blue and red stimuli on the Medmont Dark-Adapted Chromatic (DAC) perimeter will be assessed.
- 6) OCT: Change in Central Subfield Foveal Thickness (CSFT) and Change in Ellipsoid Zone (EZ) area/width will be assessed using a spectral domain optical coherence tomograph (SD-OCT) volume scan using the Heidelberg Spectralis.

Safety: The safety and tolerability of ADX-2191 in subjects with retinitis pigmentosa due to confirmed rhodopsin mutations, including P23H, will be evaluated. Adverse Event data from Screening Visit A (Visit 1) until final study visit Visit 10 will be listed (by subject) and tabulated. Any serious adverse events will be described in subject narratives. In addition, any unanticipated adverse events will be separately tabulated. A urine pregnancy test will be performed at screening for women of childbearing age.

Study Population:

Inclusion Criteria - Preoperative

- 1) Up to 8 adult patients age 18 or older of any gender
- 2) Diagnosis of retinitis pigmentosa due to rhodopsin gene mutation, including P23H, confirmed previously by a CLIA or an investigational/academic lab
- 3) Impairment on VF in the opinion of the Investigator, as determined by perimetry
- 4) Willing to participate in the study as evidenced by signing of an informed consent document

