2.2. Clinical Trial Endpoints

2.2.1. Primary Endpoints

The primary endpoint is safety and tolerability of ADX-2191.

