3. INVESTIGATIONAL PLAN

3.1. Overall Clinical Trial Design and Plan

In this open-label, non-comparator Phase II clinical trial, 8 (eight) evaluable subjects with retinitis pigmentosa due to rhodopsin mutations (including P23H) will be identified and treated with serial intravitreal injections of ADX-2191 in the worse seeing eye (“**the study eye**”). Ocular structure and function will be evaluated.

The first four subjects (Cohort A) will be treated with monthly intravitreal injections of ADX-2191 for a total of three injections; the last four subjects (Cohort B) will be treated with twice monthly intravitreal injections of ADX-2191 for a total of six injections. All subjects will be followed for a total of 16 weeks following dosing.

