6.5. Adverse Events

Any serious, unexpected adverse events (AE) believed to be due to the intervention rather than the natural disease process will prompt a filing of an adverse event form with the local IRB office and the FDA.

AEs will be collected from the time the subject signs the informed consent form through 30 days after the last dose of IP. AEs must be recorded in the CRF. The Sponsor and investigator or qualified site staff will review and evaluate AEs on an ongoing basis. See Section 8 for further detail on AE reporting.

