8.3. Recording Adverse Events

Safety assessments will include but not limited to evaluation of AEs using National Cancer Institute's Common Terminology Criteria for Adverse Events (CTCAE) Version 5.0 2017, or higher, clinical laboratory results, pregnancy testing, and vital sign measurements. If a CTCAE

grading is not listed for a specific event then the AE will be graded as mild, moderate or severe, per Section 8.4.

AEs will be recorded from the time of signing of informed consent up to the final clinical trial visit.

All AEs must be recorded in the site's clinical trial records and the AE CRF. Investigators should use correct medical terminology when recording events and avoid abbreviations.

The investigator should attempt to establish a diagnosis of the AE based on signs, symptoms, and/or other clinical information. The diagnosis, and not the individual signs/symptoms, or laboratory abnormalities, should be documented in the subject's source documents and the CRF unless the etiology of the event is unknown. If signs/symptoms cannot be medically characterized as a single diagnosis or syndrome at the time of reporting, each individual event should be recorded as an AE. If a diagnosis is subsequently established, it should be reported as follow-up information.

An assessment should be made at each visit (or more frequently if necessary) of any changes in severity, the suspected relationship to IP, the interventions required to treat it, and the outcome.

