8.6.2. Reporting Serious Adverse Events

The investigator is responsible for reporting all SAEs, regardless of causality, to the Sponsor designee within 24 hours of learning of the occurrence. The paper SAE form must be sent to the study Medical Monitor, [name], at [contact]

The reporting timeframe starts when the subject signs the informed consent or assent form through 30 days after the last IP administration. At a minimum, a description of the event and the Investigator’s judgment of causality must be provided at the time of the initial report. These preliminary reports will be followed by detailed descriptions that will include copies of hospital case reports, autopsy reports, and other documents when requested and applicable.

A follow-up SAE Report must be submitted within 24 hours of the investigator receiving the follow-up information (such as information regarding complications, progression or resolution).

An SAE that is considered completely unrelated to a previously reported event should be reported separately as a new SAE.

The original copy of the SAE Report Form and the fax confirmation sheet (or email) must be kept with the source documentation at the clinical trial site.

Follow-up information should be communicated the same way, using a new SAE Report Form stating that it is a follow-up to the previously reported SAE and giving the date of the original report. The follow-up information should describe whether the event has resolved or continues, if and how it was treated, and whether the subject continued or withdrew from clinical trial participation.

The investigator and qualified site staff should institute any supplemental investigations of SAEs based on their clinical judgment of likely causative factors. This may include clinical laboratory tests not specified in the protocol, histopathologic examinations, or consultations with specialists. The Sponsor or their designee may also request the investigator to conduct supplemental assessments.

If the SAE was not previously documented in the Investigator's Brochure and is thought to be related to IP, the Sponsor or their designee may urgently require further information from the investigator for regulatory authority reporting. The Sponsor may need to issue an investigator Notification to inform all investigators involved in any clinical trial with the same drug that this SAE has been reported.

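### The protocol gives two end points for adverse event collection, and the 30-day rule closes nominally 26 days (Cohort A) or 12 days (Cohort B) before Visit 10

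*Combined protocol and SAP*

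**What the plan says.** Safety is primary. Section 2.2.1: "The primary endpoint is safety and tolerability of ADX-2191". Section 9.2.5 lists its components as slit-lamp evaluation, dilated ophthalmoscopy and AE query, and reports treatment-emergent AEs as counts and percentages per treatment group.

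Three places stop 30 days after the last injection:
- Section 6.5: "AEs will be collected from the time the subject signs the informed consent form through 30 days after the last dose of IP".
- Section 8, opening paragraph: "AEs will be collected from the time the subject signs the informed consent form through 30 days after the last IP administration".
- Section 8.6.2, for SAEs: "The reporting timeframe starts when the subject signs the informed consent or assent form through 30 days after the last IP administration".

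Four places run to the final visit:
- Section 8.3: "AEs will be recorded from the time of signing of informed consent up to the final clinical trial visit".
- Synopsis, Safety: "Adverse Event data from Screening Visit A (Visit 1) until final study visit Visit 10 will be listed (by subject) and tabulated".
- Table 1 marks AE collection at Visit 10 for both cohorts.
- Section 7.10 lists AE collection among the Week 16 tasks, but refers the site to Section 6.5 for how to do it.

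Section 4.4 also keeps treated subjects under safety follow-up for the planned course of the trial. Section 8.7 already uses a later-of-the-two rule for pregnancies in women.

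On length of follow-up, Section 3.1 (and the synopsis) states: "All subjects will be followed for a total of 16 weeks following dosing". The synopsis gives 16 weeks of participation, and Section 3.4 gives about 16 weeks over 10 visits.

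**The concern.** The end of AE collection defines the observation period for part of the primary endpoint. The definitions of treatment-emergent events in Sections 8.5 and 9.2.5 have a start but no end, so the collection rule alone sets how long each subject is observed. The statistical analysis plan, due before database lock, cannot recover events that were never recorded.

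The conflict lies within Section 8 itself (its opening paragraph against 8.3). Section 7.10 does not resolve it, because it sends the Week 16 visit back to a section whose window has by then closed. With up to three sites, each could apply a different rule in good faith.

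For SAEs, the only specific window is the 30-day one. Section 8.6 names retinal detachment as an example of a vision-threatening SAE. One that arose after the cut-off and was first seen at Visit 10 would fall outside the timeframe for 24-hour reporting to the sponsor.

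**Working it through.** **Inputs.** Week 0 is Visit 2 (Section 7) and is the first injection (Section 6.8), so it is taken as day 0. From Table 1, the last injection is at Week 8 in Cohort A (8 × 7 = day 56) and Week 10 in Cohort B (10 × 7 = day 70). Visit 10 is at Week 16 (16 × 7 = day 112). The visit window is ±5 days from Visit 6 onward.

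**The plan's own figure.** From first injection to Visit 10 is 112 / 7 = 16.0 weeks in both cohorts, so 16 weeks is reproduced when counted from the first injection. From the last injection it is (112 − 56) / 7 = 8.0 weeks (A) and (112 − 70) / 7 = 6.0 weeks (B).

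**Gap between the two rules**, for subjects who receive every injection: gap = 112 − (last injection day + 30).

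| | Cohort A | Cohort B |
|---|---|---|
| Last injection | day 56 | day 70 |
| 30-day cut-off | day 86 | day 100 |
| Visit 10 | day 112 | day 112 |
| Nominal gap | 26 days | 12 days |
| Share of time after last injection | 26/56 = 46% | 12/42 = 29% |
| Share of time after first injection | 26/112 = 23% | 12/112 = 11% |

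**With visit windows.** The smallest gap has a late last injection and an early Visit 10; the largest has the reverse.
- A: 107 − (61 + 30) = 16 days to 117 − (51 + 30) = 36 days.
- B: 107 − (75 + 30) = 2 days to 117 − (65 + 30) = 22 days.

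In Cohort A, Visit 9 can also fall outside: a last injection on day 51 gives a cut-off of day 81, and Visit 9 may be as late as day 89.

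**Total for eight completers if every site used the 30-day rule.** 4 × 26 + 4 × 12 = 152 of 8 × 112 = 896 person-days after first injection, or 17.0%.

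**Observation time from first injection.** 86 days (A) against 100 days (B) under the 30-day rule; 112 days in both under the Visit 10 rule. With four subjects per cohort, one more subject with an event moves a percentage by 1/4 = 25 points.

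**Early stoppers.** A subject with one injection who is still followed to Week 16 under Section 4.4 would have a gap of 112 − 30 = 82 days. Section 3.6 instead brings the end-of-study visit forward to discontinuation, so this figure depends on which section governs.

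**The case against.** Much of the operative text already points to Visit 10. Table 1, Section 7.10, Section 8.3 and the synopsis all do, and no stated analysis rule drops an event recorded there. This stands: the loss is conditional on which section a site follows.

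Four stronger readings are tempting, and the documents do not support them.

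- *The primary endpoint goes unobserved after the cut-off.* Slit-lamp and dilated examinations are scheduled at Visit 10 whatever the AE window, so their findings still reach the primary safety data. Only the AE-query component is exposed.
- *A late SAE carries no reporting duty.* Section 8.6.4 requires prompt reporting to the ethics board of deaths and of SAEs possibly associated with the product, with no 30-day limit. The first paragraph of Section 6.5 requires filing with the ethics board and the FDA for serious, unexpected events attributed to the intervention, with no cut-off stated there. What lapses is the 24-hour, all-causality duty to the sponsor.
- *The cohort comparison is biased.* That depends on the time anchor. The 30-day rule gives unequal time from first injection (86 and 100 days) but equal time after the last (30 days). The Visit 10 rule gives equal time from first injection (112 days) but unequal time after the last (56 and 42 days). The AE summaries are descriptive, and no between-cohort test of AEs is specified.
- *The stated 16 weeks of follow-up is not delivered.* It is delivered from the first injection, which fits the 16-week participation in the synopsis and Section 3.4. The wording leaves the anchor open; it is not shown to be false.

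It is also true that no section expressly ends SAE reporting at Visit 10. The conflict for SAEs arises because they are AEs, and so also fall under Section 8.3 and the synopsis.

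**Conclusion.** The contradiction is real and should be corrected. The 30-day rule closes AE collection and sponsor SAE reporting nominally 26 days (Cohort A) or 12 days (Cohort B) before Visit 10. These values assume that all injections are given on their nominal days; the windows widen them to 16 to 36 and 2 to 22 days. Any loss is confined to AE-query data and the 24-hour SAE duty to the sponsor, and occurs only where the 30-day sections are followed. The 17% of person-days is therefore the nominal figure if every site did so with eight completers, not an expected loss. The more likely harm is sites collecting over different periods.

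The anchor for the 16 weeks is a separate and minor point of clarity.

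**What to change.** Give Sections 6.5, 8, 8.3 and 8.6.2 one end point for AEs and SAEs: from consent to the final visit or 30 days after the last injection, whichever comes later. Section 8.7 has this form for pregnancies in women. For subjects who receive every injection within the windows, Visit 10 is always the later date (the smallest gap is 2 days), so nominal collection would run to day 112 in both cohorts. The 30-day limb still matters for a subject whose end-of-study visit is brought forward under Section 3.6. Section 7.10 can keep its reference to Section 6.5 once that section is corrected.

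Separately, state in Section 3.1 and the synopsis that the 16 weeks run from the first injection, and that scheduled follow-up after the last is 8 weeks (Cohort A) or 6 weeks (Cohort B).

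The cost is wording in four sections, plus the clarification in Section 3.1 and the synopsis. AEs are already queried at Visits 9 and 10, so no visit or assessment is added.

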8.1. Adverse Event

An AE is any untoward medical occurrence in a patient administered an IP, which does not necessarily have a causal relationship with the IP treatment. Therefore, an AE can be any unfavorable and unintended sign, symptom, or disease temporally associated with the use of the IP, whether or not it is considered related to the IP.

Abnormal investigational findings (i.e., physical exam) should not be reported as AEs unless they are associated with clinical signs and symptoms, lead to treatment discontinuation, or are otherwise considered clinically relevant by the investigator. In cases of surgical or diagnostic procedures, the condition/illness leading to such a procedure is considered as the AE rather than the procedure itself. In case of a fatality, the cause of death is considered as the AE, and the death is considered as its outcome.

8.2. Events Not to Be Considered as Adverse Events

Pre-existing medical conditions/signs/symptoms present before the Screening Visit (Visit 1) that do not worsen in severity or frequency during the clinical trial are defined as baseline medical conditions and are not to be considered AEs.

Pregnancies are not considered AEs but must be reported, see Section 8.7.

8.3. Recording Adverse Events

Safety assessments will include but not limited to evaluation of AEs using National Cancer Institute's Common Terminology Criteria for Adverse Events (CTCAE) Version 5.0 2017, or higher, clinical laboratory results, pregnancy testing, and vital sign measurements. If a CTCAE

grading is not listed for a specific event then the AE will be graded as mild, moderate or severe, per Section 8.4.

AEs will be recorded from the time of signing of informed consent up to the final clinical trial visit.

All AEs must be recorded in the site's clinical trial records and the AE CRF. Investigators should use correct medical terminology when recording events and avoid abbreviations.

The investigator should attempt to establish a diagnosis of the AE based on signs, symptoms, and/or other clinical information. The diagnosis, and not the individual signs/symptoms, or laboratory abnormalities, should be documented in the subject's source documents and the CRF unless the etiology of the event is unknown. If signs/symptoms cannot be medically characterized as a single diagnosis or syndrome at the time of reporting, each individual event should be recorded as an AE. If a diagnosis is subsequently established, it should be reported as follow-up information.

An assessment should be made at each visit (or more frequently if necessary) of any changes in severity, the suspected relationship to IP, the interventions required to treat it, and the outcome.

8.4. Assessment of Causality and Severity

For each AE recorded, the investigator will make an assessment of causality and severity as follows:

1. Relationship to IP: The investigator must assess whether they consider an AE to be drug-related. In assessing this relationship, the investigator must use information about the drug as outlined in the Investigator's Brochure, the subject's pre-existent medical conditions/concurrent medication, and chronology of the event relative to drug administration. The following definitions will be used:
 - Definitely Related
 - Probably Related
 - Possibly Related
 - Unlikely to be related
 - Not Related

For regulatory authority reporting, only "related," or "not related" classification will be used. AEs identified as definitely, probably, or possibly, will be classified as "related." Those AEs identified as unlikely, or not related, will be classified as "not related."

2. Event Severity: The investigator will be asked to use their medical judgment to assess the severity of the AE.
3. The following are guidelines to be used by the investigator to judge the event severity of an AE:
 - Mild (Grade I) - awareness of sign or symptom, but easily tolerated
 - Moderate (Grade II) - discomfort enough to cause interference with usual activity

- Severe (Grade III) - incapacitating with inability to work or perform usual activity
 - Very Severe (Grade IV) – Vision or life-threatening; urgent intervention indicated
 - Death (Grade V) – death of subject
4. Expectedness: The expectedness of an AE should be determined based on upon existing safety information about the IP using the following explanations:
- *Unexpected*: an AE that is not listed in the IB or is not listed at the specificity or severity that has been observed.
 - *Expected*: an AE that is listed in the IB at the specificity and severity that has been observed.
 - *Not applicable*: an AE unrelated to the IP.
 - AE events that are mentioned in the IB as occurring with a class of products or as anticipated from the pharmacological/mechanical (or other) properties of the product but are not specifically mentioned as occurring with the particular product under investigation, are to be considered unexpected.
 - The investigator should initially classify the expectedness of an AE, but the final classification is subject to the determination of the Sponsor's Medical Monitor.
5. Duration: Start and end dates and times, or if continuing.
6. Frequency: whether the event is a single episode, recurrent or continuous.
7. Action taken.
8. Whether it constitutes a SAE, per definition below.
9. Outcome: resolved, resolved with sequelae, continuing, death, or unknown (only for subjects that are lost to follow-up).

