1.2. Potential Risks and Benefits

1.2.1. Potential Risks

General risks for intravitreal injection include infection, hemorrhage; precipitated angle closures; elevated intraocular pressure (IOP) with perfusion compromise; wound leak and hypotony; anaphylactic reaction to either the agent or periprocedural materials.

In addition, known risks associated with use of intravitreal methotrexate include:

- keratopathy. Therefore, all subjects will be recommended to use lubricating eye drops at a minimum of four times a day during the study period.

- mild conjunctival hyperemia (“red eye”) and slight pain at injection site. This hyperemia and/or slight pain is seen in almost all eyes receiving methotrexate and resolves within several hours.

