9.2.5. Primary Endpoint Analyses

Safety endpoints will be summarized descriptively. Safety endpoints include:

- Slit-lamp evaluation
- Dilated ophthalmoscopy
- Adverse event (AE) query (reported, elicited, and observed)

Adverse events will be summarized descriptively. Frequencies and percentages will be provided per treatment group of subjects with treatment-emergent adverse events (TEAEs), serious TEAEs, and TEAEs causing premature discontinuation. An adverse event is treatment-emergent if it occurs after the first dose of investigational treatment. Furthermore, frequencies will be given of subjects with TEAEs by system organ class, by system organ class and preferred term, by system organ class, preferred term and maximal severity, by system organ class, preferred

term and strongest relationship, and by system organ class, preferred term, maximal severity, and strongest relationship.

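### Causality is rated only against the drug, with no rating for the injection procedure, so the relationship tables cannot consistently identify treatment-caused harm or show whether it was attributed to drug or procedure

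*Combined protocol and SAP*

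**What the plan says.** Section 8.4, item 1, sets a five-level scale headed as relationship to the IP. The instruction is "The investigator must assess whether they consider an AE to be drug-related". The rater is to use drug information from the Investigator's Brochure, the subject's conditions and medications, and "chronology of the event relative to drug administration". Section 8.3 has the rating revisited at each visit, again as "the suspected relationship to IP".

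Two further rules in 8.4 depend on that rating. For regulatory authority reporting the five levels become two: "Those AEs identified as unlikely, or not related, will be classified as" not related. Expectedness is set to not applicable for "an AE unrelated to the IP".

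Section 1.2.1 separates two sources of harm. One list opens "General risks for intravitreal injection include infection, hemorrhage" and goes on to angle closure, raised intraocular pressure, wound leak and hypotony, and anaphylaxis to the agent or to periprocedural materials. A second list gives the risks of intravitreal methotrexate: keratopathy, and conjunctival hyperemia with injection-site pain.

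Section 6.5 uses different wording for filing with the IRB and FDA. It covers serious, unexpected events "believed to be due to the intervention rather than the natural disease process will prompt a filing of an adverse event form".

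Section 9.2.5 analyses safety as the primary endpoint. It counts subjects with any TEAE, with serious TEAEs and with TEAEs leading to discontinuation. It then gives frequencies in several breakdowns, the last being "by system organ class, preferred term, maximal severity, and strongest relationship".

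**The concern.** The plan recognises that the injection itself can cause harm but provides nowhere to record that judgement. A hemorrhage from the needle is caused by trial treatment. On a literal reading of 8.4 it is not drug-related. An investigator who gives weight to timing, or who regards the drug and its route as one treatment, will rate the same event as related. The protocol has no rule that settles which reading applies, and there may be up to three sites.

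Common events are affected as well as rare ones. Section 1.2.1 expects hyperemia or slight pain in almost every treated eye and lists both under methotrexate. Under Section 6.8 the same eye also receives a needle, povidone iodine and a topical or subconjunctival anesthetic. Reasonable raters could disagree about the source of the trial's most frequent event.

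What is at stake is the meaning of the strongest-relationship tables for the primary endpoint. They would mix differences between raters with differences in what subjects experienced, and a reader could not tell whether an event in the related rows was attributed to the drug or to the injection.

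**Working it through.** The plan states no figure on this point, so there is none to reproduce. The check has four steps.

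**1. How many named risks are procedural (Section 1.2.1).**
- By list entry: 6 injection entries and 2 methotrexate entries, 6/8 = 75%.
- With hyperemia and pain counted separately: 6/9 = 67%.
- With wound leak and hypotony also separated: 7/10 = 70%.
- With anaphylaxis, which may be to the agent, moved to the drug side of the entry count: 5/8 = 62.5%.

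On every count, most named risks lie on the injection side.

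**2. One needle-caused hemorrhage followed through the protocol.**

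| Step | Rater takes the item as drug only | Rater weighs timing, or treats drug and route as one |
|---|---|---|
| 8.4 relationship | Not related | Possibly, probably or definitely related |
| 8.4 two-level class (regulatory reporting) | Not related | Related |
| 8.4 expectedness | Not applicable | Judged against the Investigator's Brochure |
| 9.2.5 overall and serious TEAE counts | Counted (serious count if serious) | Counted (serious count if serious) |
| 9.2.5 strongest-relationship rows | An unrelated row | A related row |

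Both columns comply with the text. Section 6.5 asks a third question, whether the intervention caused the event, and the protocol does not say whether that word includes the procedure.

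**3. What one differently rated subject does (Sections 3.1 and 9.2.5).** Intervals are exact (Clopper-Pearson) 95%.

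| Subjects with a related TEAE | Proportion | 95% interval |
|---|---|---|
| 0 of 4 | 0% | 0% to 60.2% |
| 1 of 4 | 25% | 0.6% to 80.6% |
| 0 of 8 | 0% | 0% to 36.9% |
| 1 of 8 | 12.5% | 0.3% to 52.7% |

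The shift is 1/4 = 25 points within a cohort and 1/8 = 12.5 points overall.

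**4. Whether the design could separate drug from needle.** Planned injections are 4 × 3 = 12 in Cohort A and 4 × 6 = 24 in Cohort B, 36 in all. Each delivers 400 µg, so dose per subject is 3 × 400 = 1,200 µg against 6 × 400 = 2,400 µg. Injections and dose both double between cohorts, and there is no sham arm. A comparison of cohorts cannot separate them, so the investigator's recorded judgement is the only attribution available.

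**The case against.** The strongest reply is that little is lost. Section 9.2.5 names no related-only table. All TEAEs, serious TEAEs and discontinuation TEAEs are counted whatever their cause, and the synopsis promises a by-subject listing and narratives for serious events, which for about eight subjects is much of the safety output. Infectious endophthalmitis leads to removal under Section 4.3, and hemorrhage is an example of a vision-related serious event in Section 8.6, so both are visible without a causality rating. All of this stands.

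It can also be said that the timing criterion leads raters towards related. It permits that rating but does not require it, and that discretion is the defect.

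A further reply is that 6.5 and 8.4 do different jobs, one a filing trigger and the other a rating scale, so they do not contradict each other outright. That is fair. Their wording still needs to be aligned.

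The 25-point figure is arithmetic for any group of four, and 9.2.5 promises frequencies rather than a related percentage. That is also correct; the figure shows sensitivity and is not an estimated bias.

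Finally, the AE CRF, the Investigator's Brochure and the SAP promised in Section 9.2.8 are not in the document reviewed, and any of them might add a procedure item. A SAP alone could not supply an attribution that the CRF never collected.

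**Conclusion.** The point holds as a gap in attribution. Causality is rated only against the IP, most named risks (6 of 8 entries) are injection risks, and no rule covers injection-caused events. The strongest-relationship tables therefore cannot consistently identify treatment-caused harm, or show whether the investigator attributed it to drug or procedure. One subject rated differently moves a cohort's related proportion by 25 points. This assumes four subjects per cohort and no procedure item on the unseen CRF.

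A reader might infer three stronger claims, which the documents do not support:

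- **That procedure harms are classed as unrelated and disappear from the results.** Nothing requires that rating, and the events remain in the overall, serious and discontinuation counts. The two-level split is stated only for regulatory reporting.
- **That serious procedure events escape safety reporting.** Section 8.6.2 sends every SAE to the sponsor within 24 hours regardless of causality, Section 8.6.4 covers unanticipated problems, and the Medical Monitor has the final say on expectedness.
- **That a second rating would show whether Cohort B's events come from more drug or more needle entries.** The two rise together, and the protocol states no such aim.

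**What to change.** - **Sections 8.3 and 8.4 (item 1) and the AE CRF:** rate each AE on the existing five-point scale twice, for relationship to ADX-2191 and for relationship to the injection procedure, including anesthetic and antiseptic.
- **Section 8.4, reporting class and expectedness:** treat an event related to either as related, and assess expectedness for it. Reserve not applicable for events related to neither.
- **Section 9.2.5:** tabulate TEAEs by drug relationship, by procedure relationship and by either.
- **Section 6.5:** reconcile its reference to the intervention with 8.4, so that the filing trigger and the rating use the same terms.

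The cost is one extra CRF field and one extra table, for about eight subjects. The related count will probably rise slightly, because procedure events will now be included in it. The added field records clinical attribution and should be reported as that, not as an experimental separation of drug and needle effects.
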